We propose a randomized crossover study to compare active versus sham RIC combined with one bout of isometric hand exercise. Participants will be randomly assigned the order of the two experimental sessions: active or sham RIC. The isometric hand exercise will be performed in both sessions. The washout period between the two experimental sessions will be two to three weeks to prevent any carry-over effects. Figure 1 outlines the experimental protocol. Each session will consist of a pre-test measurement (baseline), active/sham RIC, post-RIC measurement, an isometric hand exercise and a post-exercise measurement. The total time in each session is around 3 hours including preparation. At the beginning and end of active/sham RIC, blood samples will be collected to measure changes in inflammatory mediators.

[figure not shown]

Figure 1. The experimental protocol.

Participants with chronic cSCI (n=8, ASIA Impairment Scale (AIS) A-D) and age-matched (within ± 5 years) able-bodied controls (n=8) will be recruited. Participants with cSCI must have at least partial ability to make volitional finger opposition movements (thumb and index finger) in at least one hand. Participants will be excluded if they have concurrent serious medical illness, traumatic brain injury, cardiovascular or pulmonary complications, seizure history, deep vein thrombosis, or any other issues that would increase risk of magnetic or electrical stimulation required for outcome measure assessment. We will also document medications that participants are currently using for systemic inflammation, spasticity, anxiety, or depression, which could affect nervous system excitability. One screening session will be conducted to confirm eligibility and determine the target arm in each participant. The arm with consistent responses on abductor pollicis brevis muscle (APB) induced by magnetic or electrical stimulation will be the target arm. Transcranial magnetic stimulation (TMS) will be performed to determine each subject's optimal scalp location for hand motor cortex stimulation, and to determine resting motor threshold for the APB muscle. Participants will be withdrawn if TMS-induced motor evoked potentials (MEPs) are unable to be detected at the APB muscles on either hand at stimulus intensity below 90% of maximal stimulator output. More details regarding inclusion and exclusion criteria are listed in the human subject section.

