The primary muscles assessed in this study are APB and the first dorsal interosseous (FDI) muscle on the target arm. The electrophysiological variables include intra-cortical facilitation/inhibition, corticospinal excitability and peripheral nerve conduction profile. Electrophysiological variables will be measured at pre-test measurement (baseline), post-RIC measurement (post-RIC), and post-exercise measurement (immediately after the isometric hand exercise (post-RICx-0) and 15 minute later (post-RICx-15)). The blood samples will be collected at baseline and post-RIC to measure gene expression for inflammatory mediators related to Toll-like receptor (TLR) signal pathway.

For the isometric hand exercise, subjects will be instructed to pinch a dynamometer (Anyload) with thumb and index finger at different intensities and durations. Performing volitional movements at varying intensities stimulates corticospinal circuits^{42,43}. The intensities of pinch force will be 10%, 25%, and 50% of the maximal voluntary contraction (MVC). For each intensity, durations of 2, 4, and 6 s will be employed, which resulted in nine different combinations delivered in pseudorandom order. Participants will perform 2 sets of the isometric hand exercise (18 pinches in total). The interval between each pinch will be 2 seconds, with 30 second intervals between each set.

Aim 1: To determine the effects of active versus sham RIC prior to one bout of muscle contraction exercise on motor corticospinal excitability.

Hypothesis 1A: Motor evoked potential (MEP) amplitudes at the APB muscle (Primary Outcome) will significantly increase after active RIC plus isometric hand exercise compared to sham RIC plus isometric hand exercise. Active RIC alone will not significantly increase motor evoked potential amplitudes. These trends will be similar in both cSCI and able-bodied participants.

Hypothesis 1B: Secondary electrophysiological outcomes at the APB muscle will significantly change after active RIC plus isometric hand exercise compared to sham RIC plus isometric hand exercise. Short-interval and long-interval cortical inhibition will decrease; intracortical facilitation will increase. Active RIC alone will not significantly change these outcome measures. These trends will be similar in both cSCI and able-bodied participants.

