We hypothesize that RIC might synergize with motor task learning via increased corticospinal excitability at supraspinal level. In order to test our hypothesis, we select an isometric hand exercise as the motor training task in this pilot study. The reason is that several studies have demonstrated immediate and transient increased MEPs as a result of post-exercise facilitation in able-bodied participants after a short period of repetitive contraction exercise in thenar muscle⁴⁴, wrist muscle⁴⁵, forearm⁴⁶ and leg^{47,48}. Additionally, the various combinations of the intensity and the duration of pinch movements in our study, as well as the use of an intrinsic hand muscle, theoretically involves more cortical attention, which should magnify the likelihood of supraspinal neuroplasticity^{42,43,49}. We will test MEPs at baseline, post-RIC, post-RICx-0 and post-RICx-15. We expect to observe further increased MEPs of the APB thenar muscle at post-RICx due to the synergistic effects of active RIC on isometric hand exercise compared to sham RIC. Likewise, we expect that intracortical inhibition and intracortical facilitation of the APB muscle will decrease and increase, respectively. We also anticipate similar responses of all electrophysiological outcomes in both participants with cSCI and able-bodied participants.

Method: We will conduct electrophysiological measurements at four time points: baseline, post-RIC, post-RICx-0 and post-RIC-15. The post-RIC measurement allows us to first observe whether RIC-alone acutely affects corticospinal excitability. In addition, the 15-minute follow-up measurements (post-RICx-15) will allow us to investigate if the exercise effects will last longer due to active versus sham RIC. In order to localize changes on the pathway from the motor cortex to muscle, the electrophysiological outcomes include changes of intra-cortical facilitation/inhibition, peak-to-peak amplitude of MEPs at 120% resting motor threshold (RMT), and peripheral nerve profile including M/F waves. We have and already use all the major equipment necessary for outcome assessments, including a MagPro X100 TMS system (MagVenture), Digitimer peripheral nerve stimulators (Digitimer), surface EMG pre-amplifiers (Motion Lab Systems), and data acquisition boards (National Instruments).

Peak-to-Peak Amplitude of Motor Evoked Potentials at 120% intensity of Resting Motor Threshold (MEP₁₂₀):

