The optimal scalp location for APB will be determined at the screening session and stored in our Brainsight TMS Navigation system (Rogue Resolutions) for later use in each experimental session. After navigating to the optimal stimulation spot, the RMT, used for calculating single- and paired-pulse stimulation of the APB will be determined by the lowest TMS intensity at which an MEP could be induced with at least 5 of the 10 stimuli with peak to peak amplitude of 50-100 μ V at rest. The single-pulse TMS will be applied at 120% RMT to induce and record peak-to-peak amplitude of MEP₁₂₀.

Cortical inhibition and facilitation: Paired-pulse TMS will be used to measure short interval cortical inhibition (SICI), long interval cortical inhibition (LICI) and intra-cortical facilitation (ICF)⁵⁰. Paired-pulse TMS includes a conditioning (CS) and test stimulus (TS) separated by a specified interstimulus intervals (ISI). The configuration for measuring SICI, LICI and ICF in this study are as follows⁵¹⁻⁵⁴:

- SICI: CS = 90% RMT, TS = 120% RMT, ISI = 3 ms
- LICI: CS = 120% RMT, TS = 120% RMT, ISI = 100 ms
- ICF: CS = 90% RMT, TS = 120% RMT, ISI = 12 ms

Peripheral Nerve Profile: Supramaximal electrical stimulation will be delivered at median and ulnar nerves at wrist level. The peripheral nerve profile includes the latency and the peak-to-peak amplitude of the M/F waves. The peak-to-peak amplitude of the M waves will be used to normalize the MEP₁₂₀ at each time point to ensure that changes of corticospinal excitability are not due to peripheral variation⁵⁰.

Data Analysis:

Corticospinal Excitability: The primary outcome will be MEP₁₂₀ on APB (primary outcome muscle) and FDI muscles. The MEP₁₂₀ will be first normalized to peak-to-peak amplitude of M waves to take account of the peripheral variation. The changes of MEP₁₂₀ at post-RIC, post-RICx-0 and post-RICx-15 will be expressed as percentage of the changes compared to baseline MEP₁₂₀. The SICI, LICI and ICF will also be expressed as percentage of the changes compared to baseline in each value.

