Statistical Analysis: Electrophysiological outcomes will be compared after RIC and after the isometric hand exercise relative to baseline values. Descriptive analysis will be computed first for all outcomes variables to test the distribution of the data and correlation tests will be performed to check the independence among the outcome variables. A three way 2 (cSCI, able-bodied) by 2 (RIC, sham) by 3 (post-RIC, post-RICx-0, post-RICx-15) mixed-ANOVA will be used to analyze MEP₁₂₀ and intra-cortical facilitation/inhibition. If the data is not normally distributed and the assumptions of the ANOVA are not met, Wilcoxon signed rank tests will be used instead. Post hoc pairwise comparisons will be performed using the Bonferroni adjustment, if there are any main or interaction effects within the three independent variables (group, active/sham RIC and time points).

Potential Pitfalls/Alternative approaches/Future Directions: Applying RIC on motor task learning is relatively new area with little preliminary data – therefore, our primary hypothesis that RIC may promote motor task learning via increasing corticospinal excitability is highly speculative. Additionally, the effects of RIC and acute post-exercise facilitation have mostly been shown in able-bodied participants, and there are no published data in the SCI population that measured corticospinal excitability as a mechanism for acute post-exercise facilitation. Therefore, individuals with SCI might demonstrate uncertain responses toward RIC and the isometric hand exercise than that exhibited in able-bodied participants. The inconsistent injury level and the residual nerve circuits among participants with cSCI might result in the wide variability of the outcomes. Nevertheless, although our hypotheses are speculative, the proposed study is designed to provide clear answers via observing the responses in participants with cSCI and able-bodied participants. If this brief isometric hand exercise cannot lead to significantly increased MEPs in participants with cSCI, our next step might test RIC in combination with more advanced interventions such as non-invasive paired stimulation, a technique that our research team is actively studying in other protocols. Finally, if the pilot study shows a significant synergistic effect of RIC on the isometric hand exercise task, our future goal will be coupling RIC with more prolonged rehabilitation training to promote long-term effects.

[figure not shown]

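### Session order is randomised with no stated balance, and none of the three analysis models accounts for period

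*Combined protocol and SAP*

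**What the plan says.** - **Order** (Approach, Overview): "Participants will be randomly assigned the order of the two experimental sessions: active or sham RIC". No block, stratum or sequence ratio is given for the two groups of 8. The human subject section is not part of the document; the protocol cites it only for eligibility details.
- **Washout** (same section): "The washout period between the two experimental sessions will be two to three weeks to prevent any carry-over effects".
- **Session structure** (same section): "Each session will consist of a pre-test measurement (baseline), active/sham RIC, post-RIC measurement, an isometric hand exercise and a post-exercise measurement".
- **Aim 1 outcome** (Data Analysis): changes in motor evoked potential amplitude "will be expressed as percentage of the changes compared to baseline".
- **Aim 1 model** (Statistical Analysis): "A three way 2 (cSCI, able-bodied) by 2 (RIC, sham) by 3 (post-RIC, post-RICx-0, post-RICx-15) mixed-ANOVA". If the assumptions fail, "Wilcoxon signed rank tests will be used instead".
- **Aim 2 model**: group, condition and time, with baseline kept as a level of time.
- **Aim 3 model**: condition by four phases including baseline, fitted in each group of 8 separately. Pain uses the same model.

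Period and sequence appear in none of these analyses.

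**The concern.** In a two-session crossover, active and sham are compared across different sessions. If people respond differently the second time, that difference is mixed into the active-sham contrast unless the order is balanced or the analysis allows for it. The washout addresses carry-over, which is a separate problem.

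The documents report no period effect, but two sources are plausible.
- **Aim 1.** The rationale says that the varied pinch task "theoretically involves more cortical attention, which should magnify the likelihood of supraspinal neuroplasticity". Session 2 repeats that task, so attention and response may differ. An effect of this kind would show only after exercise, not at post-RIC, which has its own hypothesis: "Active RIC alone will not significantly increase motor evoked potential amplitudes".
- **Aim 3.** Pain, peak heart rate and peak blood pressure could differ at a second cuff exposure.

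For Aim 2 the documents suggest no source.

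Lost power matters here because some hypotheses predict no difference. Hypothesis 3A is one, and it concerns safety in a population for which the protocol says no data exist. An inflated residual makes such a prediction easier to appear to confirm.

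**Working it through.** **Inputs.** From the documents: 8 + 8 participants, two sessions, random order. They give no alpha, SD, effect size, power or period effect, so there is no figure of the plan's own to reproduce. Assumed: two-sided 5% test; unit = SD of the paired active-minus-sham difference; true effect τ = 0.75 for power; period effect π (session 2 minus session 1, in the within-session response) = 0, 0.25, 0.5 or 0.75. Power and type I error come from 200,000 simulated trials per split.

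**What cancels.** A shift s in a whole session drops out of a change score: (post + s) − (baseline + s) = post − baseline. With percentage change this is approximate. A shift π in the response itself stays. The paired difference has mean τ + π if active comes second and τ − π if it comes first.

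**Bias.** With n1 people in one order and n2 in the other, the unadjusted mean is off by π × (n1 − n2)/n. At 6:2 the factor is 4/8 = 0.5; at 12:4 it is 8/16 = 0.5. For π = 0.25, 0.5 and 0.75 the bias is 0.125, 0.25 and 0.375 SD. The mean of the two sequence means is [(τ + π) + (τ − π)]/2 = τ, with no bias at any split.

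**Power with balanced order, τ = 0.75** (t-test, n − 1 df unadjusted, n − 2 adjusted)

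| π | 8:8 unadjusted | 8:8 adjusted | 4:4 unadjusted | 4:4 adjusted |
|---|---|---|---|---|
| 0 | 80% | 80% | 45% | 43% |
| 0.25 | 78% | 80% | 42% | 43% |
| 0.5 | 72% | 80% | 35% | 43% |
| 0.75 | 62% | 80% | 26% | 43% |

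The loss comes from the residual. At balance the unadjusted standard error is inflated by √(1 + π²n/(n − 1)); for n = 16 and π = 0.5 this is √(1 + 0.25 × 16/15) = 1.125.

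**Type I error with unbalanced order**

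| π | 12:4 unadjusted | 6:2 unadjusted | Adjusted, either split |
|---|---|---|---|
| 0.25 | 6.9% | 5.6% | 5.0% |
| 0.5 | 11.8% | 6.8% | 5.0% |
| 0.75 | 17.5% | 7.9% | 5.0% |

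The signed rank test at 12:4 with π = 0.5 has type I error 10.4%.

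**Chance of imbalance, if randomisation is simple (not stated).** 6:2 or worse in one group: 74/256 = 28.9%. In at least one of the two groups: 1 − (1 − 0.289)² = 49%. 12:4 or worse among all 16: 7.7%. Averaged over all orders, unadjusted type I error is 5.0 to 5.1% for π up to 0.5 and mean bias is zero.

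**Which term is needed.** Bias with π = 0.5:

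| Contrast | No period term | Period main effect | Period + period-by-time |
|---|---|---|---|
| Aim 2 condition-by-time, 6:2 or 12:4 | 0.25 | 0.25 | 0 |
| Aim 3 inflation phase, 6:2 | 0.25 | 0.25 | 0 |
| Aim 1 post-RIC, 12:4 | 0 | −0.167 | 0 |
| Aim 1 both post-exercise times, 12:4 | 0.25 | 0.083 | 0 |

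The Aim 1 rows assume an effect only after exercise. A main effect then subtracts the average bias, (0 + 0.25 + 0.25)/3 = 0.167, from every time point. The Aim 2 row puts the effect on the post measurement only, and the Aim 3 row puts it in inflation only. At 4:4 and 8:8 every entry is zero.

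**The case against.** - **No period effect is documented.** The Aim 1 rationale does not say that attention falls or rises with repetition. The task is 18 pinches, repeated two to three weeks later. Aim 3 cites stable heart rate and blood pressure in other populations, and limited pain sensation after cervical injury weakens the pain example in that group. This stands, and it is why every size above is an assumption.
- **The largest figures do not coincide.** The frequent imbalance (6:2 within a group) gives type I error of only 5.6 to 7.9%. The 17.5% needs both a 12:4 split and a 0.75 SD period effect. A split of 10:6 or closer has probability 79% under simple randomisation, and at 8:8 and 10:6 unadjusted type I error is at or below about 5%. This also stands, although conditional bias remains at 10:6.
- **Adjustment without blocking can lose power.** Averaged over simple randomisation at π = 0.25, it lowers power from 77.5% to 76.7% (n = 16) and from 42.7% to 38.9% (n = 8). This is correct, so the two changes belong together.
- **The calculation uses one paired contrast, not the full ANOVA with its Bonferroni step.** True. Keeping group in the model, the sequence term takes the degrees of freedom from 14 to 13 and the effect detectable with 80% power from 0.753 to 0.758 SD, so the cost stays trivial.
- **The after-exercise-only pattern in Aim 1 is an inference.** The cuff exposure precedes post-RIC too. If the effect were equal at all three times, a period main effect would be enough for Aim 1. Adding period-by-time covers both patterns.

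None of this supplies the missing balance or the missing adjustment.

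**Conclusion.** The concern holds as a cheap improvement, minor to moderate in weight. The planned analysis is valid on average over the randomisation. What it lacks is protection for the one order that is realised. If that order is unbalanced, the contrast is biased by up to half the period effect at splits as uneven as 6:2 or 12:4, and by more beyond that. If it is balanced, there is no bias but power falls. The gain is small at a period effect of 0.25 SD and material from about 0.5 SD. Whether an effect of that size exists cannot be judged from the documents.

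**What to change.** 1. **Block the order 4:4 within each group.**
2. **Adjust for sequence.** At each post-baseline time point or phase, take each person's active-minus-sham difference in change from session baseline. Estimate the effect as the mean of the two sequence means (sequence coded ±1, group kept for Aims 1 and 2). In the mixed models the equivalent is period and period-by-time; a period main effect alone is not enough.
3. **Fallback, given blocked order.** For the pooled 8:8 contrast, compare session-1-minus-session-2 differences between sequences by rank-sum test. Within a 4:4 group the planned signed rank test can stay, because blocking already balances it. There the smallest two-sided rank-sum p is 2/70 = 0.029, which cannot meet even 0.05/2 = 0.025; at 6:2 it is 2/28 = 0.071.
4. **If allocation is complete**, report the realised split by group and give the sequence-adjusted result beside the planned one.

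**Cost with no period effect (τ = 0.75).** With blocked order, power goes from 80.1% to 79.7% at 8:8 and from 44.9% to 43.0% at 4:4. Adjustment at unblocked splits costs more: 80.1% to 67.6% at 12:4 and 44.9% to 34.0% at 6:2. The rank-sum test loses nothing at 8:8 (77% against 76% for signed rank). At 4:4 it is weaker (29% against 39%), drawing level at a period effect of 0.5 SD. No extra participants or measurements are needed. None of this corrects carry-over.

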Figure 2. Illustration of electrophysiological outcomes used to localize changes of excitability from cortex to peripheral nerve.

Aim 2: To investigate effects of active versus sham RIC on systemic inflammatory mediators in individuals with cSCI.

Hypothesis 2A: The gene expression of inflammatory mediators will significantly decrease after active RIC compared to the sham RIC in participants with cSCI.

Hypothesis 2B: The trends of inflammatory mediator change will be similar in both participants with cSCI and able-bodied participants.

Our collaborator [name] and others have demonstrated elevated inflammatory mediators in persons with chronic SCI⁵⁵⁻⁵⁷. Our objective here is to profile systemic immune responses to determine if RIC has anti-inflammatory effects in cSCI and able-bodied participants. [name] (see letter of support) recently demonstrated broad changes in inflammatory gene expression in persons with chronic SCI, which was particularly evident in persons with higher level injuries⁵⁷. Specifically, they found elevated members of the Toll-like receptor 2/4 (TLR) signaling pathway, metalloproteinases (ADAM10), caspases (CASP1, 3, 8) and chemokine gene families. Previously, it was shown in able-bodied adults that RIC (3x5 min) resulted in reduced levels of inflammatory mediators in the blood at 15min and 24h later⁵⁸. Specifically, members of the same genes and gene families elevated in persons with chronic SCI⁵⁷ were reduced by RIC in able bodied individuals: TLR signaling pathway, TNF receptor pathway, MAP kinases, apoptosis pathway (CASP8), chemokines, T cell signaling molecules, metalloproteinases and leukocyte adhesion molecules⁵⁸. Here, we will test if RIC in the current experimental paradigm has a similar anti-inflammatory effect in persons with SCI as has been documented in the able-bodied population.

Methods: Blood samples (3cc) will be collected before the active/sham RIC cycle and 15 minutes after the end of RIC at the post-RIC measurement. According to previous research, the alteration of inflammatory mediators should occur after 15 minutes⁵⁸.

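### The hypotheses of group similarity and of no effect (1A, 1B, 2B, 3A) are paired only with difference tests, so the plan can support them only through non-significance

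*Combined protocol and SAP*

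**What the plan says.** Under Aim 1, Hypothesis 1A predicts a larger rise in MEP amplitude (the primary outcome) after active than after sham RIC plus exercise. It then adds two predictions of a different kind: "Active RIC alone will not significantly increase motor evoked potential amplitudes", and "These trends will be similar in both cSCI and able-bodied participants". Hypothesis 1B repeats the second and says of the intracortical inhibition and facilitation measures: "Active RIC alone will not significantly change these outcome measures".

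Under Aim 2, Hypothesis 2B reads: "The trends of inflammatory mediator change will be similar in both participants with cSCI and able-bodied participants". Under Aim 3, Hypothesis 3A predicts that HR, BP and SaO2 will not differ across baseline, inflation, deflation and post-RIC, in active and sham sessions, in either group.

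The planned inference is as follows.

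- **Aim 1:** "A three way 2 (cSCI, able-bodied) by 2 (RIC, sham) by 3" (the three post-baseline time points) mixed ANOVA. The Data Analysis section expresses the outcomes as percentage change from baseline.
- **Aim 2:** a 2 by 2 by 2 mixed ANOVA in which baseline versus post-RIC is itself a factor.
- **Aim 3:** a 2 by 4 repeated measures ANOVA, run separately in each group.
- **All three aims:** Wilcoxon signed rank tests if the ANOVA assumptions fail.

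The sample is given in the Approach overview: "Participants with chronic cSCI (n=8, ASIA Impairment Scale (AIS) A-D) and age-matched (within ± 5 years) able-bodied controls (n=8) will be recruited". The documents contain no definition of similar, no margin, no confidence-interval criterion and no power calculation.

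**The concern.** A test of difference can reject equality but cannot establish it. When a hypothesis predicts similarity or no effect and the only tool is such a test, the only result that can count in its favour is a non-significant one. A small study produces that result readily, whether or not the hypothesis is true. For RIC alone the link is explicit, because the predictions themselves are worded in terms of significance.

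Three things are at stake.

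- **Group similarity.** The Potential Pitfalls text under Aim 1 expects uncertain responses and wide variability in cSCI, yet says that observing both groups should give clear answers.
- **RIC alone.** The expected gain after exercise is described as synergy between RIC and exercise. If RIC alone has a modest effect that goes undetected at post-RIC, a merely additive effect after exercise could be described as synergistic.
- **Haemodynamics.** Aim 3 says that no data describe the safety of RIC in people with SCI. A statement of no difference would carry weight there.

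**Working it through.** The plan states no power figure, so there is none to reproduce.

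**Inputs from the documents.** 8 cSCI and 8 able-bodied participants; active versus sham compared within person ("We propose a randomized crossover study to compare active versus sham RIC combined with one bout of isometric hand exercise").

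**Assumptions, because the documents are silent.** Two-sided alpha 0.05; no dropout; normal data with equal SD in the two groups; true effects of 0.5 to 1.5 SD. The SD is that of each person's active-minus-sham contrast. Each calculation is for a single contrast on a single outcome, so in Aim 2 it is per gene.

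**Which contrast answers which hypothesis**

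- *2B.* Time is a factor in the Aim 2 model, so similarity of change is the group x condition x time term. It equals a two-sample t test on (active post-RIC − active baseline) − (sham post-RIC − sham baseline), 8 versus 8, 14 df. The group x condition term would average over baseline and post-RIC and so answers a different question.
- *1A and 1B, similarity.* The data are already changes from baseline. The relevant quantity is the between-group difference in the active-minus-sham change at each time point, again 8 versus 8. The overall group x condition term would mix post-RIC with the two post-exercise points.
- *1A and 1B, RIC alone.* Active minus sham at post-RIC, within person: n = 8 in one group (7 df), or 16 people pooled with group in the model (14 df).

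**Power.** Noncentral t, with noncentrality

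- between groups: d × √(8/2) = 2d, critical t(14) = 2.145;
- within one group: d × √8 = 2.83d, critical t(7) = 2.365;
- pooled: d × √16 = 4d, critical t(14) = 2.145.

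Probability of a non-significant result (1 − power):

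| True effect (SD) | Group difference, 8 vs 8 | RIC alone, one group of 8 | RIC alone, pooled 16 |
|---|---|---|---|
| 0.5 | 85% | 77% | 54% |
| 0.8 | 68% | 50% | 15% |
| 1.0 | 54% | 32% | 4% |
| 1.2 | 39% | 17% | 1% |
| 1.5 | 20% | 5% | under 1% |
| Effect at which power is 50% | 1.05 SD | 0.80 SD | 0.53 SD |

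If the post-RIC comparison is Bonferroni-adjusted over three time points (alpha 0.05/3), the 50% points for RIC alone move to 1.06 SD in one group and 0.67 SD pooled. A pooled 0.8 SD effect is then missed 32% of the time (1 − 0.683).

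**95% CI half-widths**

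- Group difference: 2.145 × √(2/8) = 1.07 SD.
- RIC alone, one group: 2.365/√8 = 0.84 SD.
- RIC alone, pooled: 2.145/4 = 0.54 SD.

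**What a margin could deliver.** The table gives the chance of showing equivalence when the true difference is zero, by two one-sided 5% tests (90% CI inside the margin).

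| Margin (SD) | Groups, 8 vs 8 | RIC alone, pooled 16 |
|---|---|---|
| 0.5 | 0.1% | 23% |
| 0.8 | 6% | 84% |
| 1.0 | 23% | 97% |
| 1.5 | 77% | over 99% |

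A 95% CI rule is stricter, so these are upper figures for it.

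**Fallback.** A signed rank test is paired. It can compare active with sham within a person, but it cannot compare two independent groups. If it replaces the mixed ANOVA, the similarity predictions of Aims 1 and 2 have no test at all.

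**The case against.** A fair defence has four parts.

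1. *This is a proof-of-concept study.* It calls its hypotheses speculative. The superiority claim in 1A does not depend on the similarity clauses, and the next steps under Aim 1 depend on significant MEP or synergy findings, not on similarity. This stands, and it limits the consequences.

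2. *No passage says that a non-significant interaction will be reported as similarity.* A reader might infer that the investigators have committed to that; the documents do not say so. What they do show is that no other route to supporting these hypotheses has been provided.

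3. *The miss rates depend on the assumed effects.* This stands too. A reader might infer that non-significance is the likely outcome for every one of these hypotheses whenever it is false. That is not supported. For the group comparison the pattern reverses above about 1.05 SD. For RIC alone the crossover helps: pooled over 16, a 0.8 SD effect is missed only about 15% of the time. Nor does a no-effect prediction for RIC alone extend to inflammation, where 2A predicts the opposite: "The gene expression of inflammatory mediators will significantly decrease after active RIC compared to the sham RIC in participants with cSCI".

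4. *Margins would be hard to set.* Aim 2 uses a multi-gene array, and 8 per group would rarely meet a narrow margin. This is a good reason not to require margins. It is not a reason to let non-significance stand in for them.

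**Conclusion.** The concern holds as a mismatch between hypothesis and analysis. The similarity and no-effect clauses of 1A, 1B, 2B and 3A have only difference tests behind them, so the plan can support them only by failing to find something.

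The weakness is greatest for group similarity. The interval will extend about 1.07 SD either side of the estimate, and true differences up to about 1 SD are more likely than not to be non-significant. It is smaller for RIC alone analysed over all 16 people, where only effects below about 0.53 SD (0.67 SD with Bonferroni) are more likely missed than found. Aim 3 is analysed within each group of 8, so a single active-minus-sham contrast there has the one-group precision.

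The percentages rest on the assumed alpha, effect sizes and equal SDs; the mismatch itself does not. The active-versus-sham superiority comparison of the primary outcome is unaffected.

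**What to change.** Restate these clauses as estimation, and report with 95% CIs:

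- (a) Aim 1: the between-group difference in the active-minus-sham change at each time point;
- (b) Aim 1: the active-minus-sham difference at post-RIC;
- (c) Aim 2: the group x condition x time contrast, that is, the between-group difference in active-minus-sham change from baseline;
- (d) Aim 3: the active-minus-sham haemodynamic changes in each group.

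Add a sentence that a non-significant result will not be reported as similarity or absence of effect. Then choose one of two routes. Either label these hypotheses descriptive, or draw the conclusion only when the CI lies inside a margin fixed beforehand and otherwise report not determined. A margin would have to be set before any data are examined, and the Project timeline starts analysis after the first two or three participants. Per-gene margins for Aim 2 are not needed if the descriptive route is taken.

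The cost is wording and some analysis output, with no extra participants or measurements. The downside is that group similarity will probably be reported as not determined.
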